3.9. TREATMENT ASSIGNMENT & BLINDING

3.9.1. Treatment Assignment

The study will be conducted at multiple investigative sites and will likely involve various numbers of subjects at each site. The study will have a competitive enrollment but the number of randomized subjects from each site will be capped at 40. Activation of investigational sites will be centrally controlled by an Interactive Web Response System (IWRS). Subject randomization will be deactivated for all sites when the planned number of subjects is met. However, if a potential subject is in wash-out already and wishes to continue with the study, the subject will be allowed to continue and, if eligible, to be randomized.

Eligible subjects who have completed the wash-out of oral hypoglycemic agent other than metformin and have met all study inclusion/exclusion requirements are to be randomized in a 1:1 ratio to receive active bexagliflozin with placebo glimepiride or active glimepiride with placebo bexagliflozin. Subjects will be assigned to treatment groups in sequential order as they qualify for the study. Randomization will be stratified according to baseline (Visit V5) HbA_{1c} (< 8.5% or ≥ 8.5%), treatment background

(metformin-only or metformin-and-OHA), and Visit V5 eGFR (≥ 90 or < 90 and ≥ 60 mL/min/1.73 m²).

3.9.2. Blinding

This is a double-blind, double dummy study. The sponsor, investigators, study coordinators, pharmacists, study subjects, the cardiovascular adjudication committee and the diabetic ketoacidosis committee will be blinded to the study medication.

To maintain blinding of the individual treatment assignment, the results of urinary glucose testing will not be made available to any study personnel or subjects. If knowledge of the test substance is needed to manage a subject's condition, the investigator will contact the IWRS to obtain the treatment assignment. If unblinding occurs for any reason, the time and reason for breaking the blind will be recorded on the case report form (CRF) and the sponsor must be notified within 24 hours.

A designated statistician who is not involved with the study operation will hold the treatment codes. The unblinded treatment information can be provided to the Data and Safety Monitoring Board (DSMB) to facilitate the evaluation of any clinically important increase in the rate of a serious suspected adverse reaction or to the designated safety contact when the treatment information is required to determine if an expedited safety report must be submitted to regulatory agencies.

The treatment assignment will continue to be withheld from the cardiovascular adjudication committee and diabetic ketoacidosis adjudication committee members until all global investigational studies are completed and final analyses to assess cardiovascular and ketoacidosis risks are conducted.

3.10. ADMINISTRATION OF STUDY MEDICATION

The following investigational products will be used for oral administration:

- Bexagliflozin tablets, 20 mg: tablets containing 20 mg of bexagliflozin
- Bexagliflozin tablets, placebo: tablets containing no bexagliflozin

Active comparator will be:

- Glimepiride capsules, 2 mg: capsules containing 2 mg of glimepiride
- Glimepiride capsules, 4 mg: capsules containing 4 mg of glimepiride
- Glimepiride capsules, 6 mg: capsules containing 6 mg of glimepiride
- Glimepiride capsules, placebo: capsules containing no glimepiride

Bexagliflozin tablets, 20 mg or placebo, should be taken with 250 mL of water in the morning prior to eating or drinking. On the day of scheduled clinic visits when there is

fasting and blood is to be drawn, administration of bexagliflozin should be delayed until after blood is drawn and taken in the clinic or at home prior to the first meal with 250 mL of water.

Glimepiride capsules, 2, 4 or 6 mg or placebo, should be taken once daily with the first meal. On the day of scheduled clinic visits when there is fasting and blood is to be drawn, administration of glimepiride shall be withheld until the first meal.

3.11. STUDY PROCEDURES AND FLOWCHART

The activities that must be performed at each clinic visit listed below are presented in Table 1.

A visit window of ± 3 days is allowed for all visits except Visit 6. V6 is the day of randomization and the basis for the visit window.

The study staff will contact each subject prior to a scheduled clinic visit to confirm the time of the visit and to remind the subject of proper fasting practice. A subject must be queried to assess compliance with an approximately 10 hours fast prior to blood draw to ensure the FPG and triglycerides values can be accurately determined. If a subject has not fasted for approximately 10 hours, the subject must return as soon as can be arranged (within 1 week) to provide a specimen after proper fasting. Blood samples will be transported to the central lab for analysis.

Table 1 Schedule of Events

	Screening	Wash-out		Run-in		Efficacy Assessment									Safety Extension			Follow-up
Visit number	V1	V2	V3	V4	V5	V6	V7	V8	V9	V10	V11	V12	V13	V14	V15	V16	V17	V18
Time to Randomization Visit (wk)	-11	-8	-6	-2	-0.5	0	2	4	6	12	24	36	48	60	72	84	96	98
Off-site phone visit			X													X		
Informed Consent	X																	
EQ-5D-3L						X					X			X			X	
Screening for I/E criteria	X	X			X													
Demographics and medical history	X																	
Diet & exercise counseling		X		X														
Physical exam					X									X				X
Abbreviated physical exam	X								X		X	X	X		X		X	
Record height	X																	
Record body weight	X				X				X	X	X	X	X	X	X		X	X
Dispense diary & glucometer		X		X														
Diary & glucometer record review			X	X	X	X	X	X	X	X	X	X	X	X	X	X	X	X
Start wash-out		X																
Dispense Run-in Medication				X														
Randomization						X												
Vital signs	X			X	X		X	X	X	X	X	X	X	X	X		X	X
ECG	X				X						X			X			X	
Discontinue non-metformin OHA		X																
Dispense bexagliflozin						X				X	X	X	X	X	X			
Dispense glimepiride						X	X	X	X	X	X	X	X	X	X			

This document is proprietary and confidential to INC Research LLC.

Visit number	Screening	Wash-out		Run-in		Efficacy Assessment									Safety Extension			Follow-up
	V1	V2	V3	V4	V5	V6	V7	V8	V9	V10	V11	V12	V13	V14	V15	V16	V17	V18
Time to Randomization Visit (wk)	-11	-8	-6	-2	-0.5	0	2	4	6	12	24	36	48	60	72	84	96	98
Blood draw for clinical lab test	X				X				X	X	X	X	X	X	X		X	X
Urine collection	X				X				X	X	X	X	X	X	X		X	X
AE		X	X	X	X	X	X	X	X	X	X	X	X	X	X	X	X	X
Con Med		X	X	X	X	X	X	X	X	X	X	X	X	X	X	X	X	X
Hematology	X				X				X		X		X	X			X	X
Serum chemistry electrolytes	X				X				X		X		X	X			X	X
Fasting Plasma Glucose	X				X				X	X	X	X	X	X	X		X	X
HbA _{1c}	X				X					X	X	X	X	X	X		X	X
Lipids	X				X						X			X			X	X
Urinalysis	X				X				X	X	X	X	X	X	X		X	X
Urine pregnancy test (UPT)	X				X				X	X	X	X	X	X	X		X	X

4. ENDPOINTS

4.1. PRIMARY EFFICACY ENDPOINT

- Change from baseline to week 60 in HbA_{1c} compared to glimepiride

4.2. SECONDARY EFFICACY ENDPOINTS

- Change from baseline to week 60 in body weight in subjects with baseline body mass index (BMI) ≥ 25 kg/m²
- Change from baseline to week 60 in SBP in subjects with baseline SBP ≥ 140 mmHg
- Difference in proportion of subjects with ≥ 1 severe or documented symptomatic hypoglycemia events over 96 weeks
- Change from baseline to week 60 in HbA_{1c}

4.3. OTHER EFFICACY ENDPOINTS

- Change over time in proportion of subjects achieving HbA_{1c} $< 7.0\%$
- Change over time in body weight
- Change over time in FPG
- Change over time in SBP
- Change over time in HbA_{1c}
- Difference in proportion of subjects with ≥ 1 severe or documented symptomatic hypoglycemia events over time

4.4. SAFETY ENDPOINTS

- Adverse events of interest are UTI, pyelonephritis urosepsis, GMI, diuretic effects including hypovolemia, hypotension episodes, hypoglycemia, hepatotoxicity, MACE, fractures, malignancies, hypersensitivity reactions, acid-base disorders including diabetic ketoacidosis, rash, and renal failure events
- Laboratory testing, including hematology, serum chemistry, and urinalysis
- Physical examination
- 12-lead ECG
- Vital signs
- Concomitant medication use

4.5. OTHER ENDPOINTS

- Health-related quality of life instrument, EQ-5D-3L

5. ANALYSIS SETS

5.1. SCREENED ANALYSIS SET

The Screened Analysis Set will include all subjects screened for eligibility prior to randomization. The screened population will include screen failures. Unless specified otherwise, this population will be used for summaries of subject disposition.

5.2. SAFETY ANALYSIS SET

All subjects who are randomized and take at least one dose of double-blind study medication will be included in the Safety Analysis Set. Safety analyses will be based on the medication that was taken first. The Safety Analysis Set is the primary analysis set for safety evaluation.

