3.3.2 Treatment Period

The double-blind treatment period will start at randomization and last 96 weeks. A total of 420 subjects of 210 subjects per group will be randomized in a 1:1 ratio to the two groups as shown in [Table 1](#).

Table 1. Treatment Groups and Assigned Treatment

Treatment Group	Treatment
1	Bexagliflozin tablets, 20 mg, (once daily P.O.) Glimepiride capsules, placebo, (once daily P.O.)
2	Bexagliflozin tablets, placebo, (once daily P.O.) Glimepiride capsules, 2, 4 or 6 mg, (once daily P.O.)

Randomization will be stratified by HbA1c at Visit V5 ($\leq 8.5\%$ vs. $> 8.5\%$), treatment background (metformin-only vs. metformin-and-OHA), and baseline estimated glomerular filtration rate (eGFR) at screening visit (V1) ($eGFR \geq 90$ vs. < 90 and ≥ 60 mL/min/1.73 m²). At the start of the treatment period, each subject will be provided with bexagliflozin tablets, glimepiride capsules, dosing instructions, and a glycemic control diary in which to record SMBG measurements. Symptoms and blood sugars related to the occurrence of hyperglycemia, hypoglycemic events or symptoms that may suggest ketoacidosis will be recorded. Bexagliflozin tablets, 20 mg or placebo, will be orally administered once daily prior to the first meal; glimepiride capsules, 2, 4, or 6 mg or placebo, will be taken once daily with the first meal. Background medication metformin shall be taken at an unchanged dose and frequency taken at screening throughout the entire study.

Each subject will be instructed to return to the clinic at weeks 0, 2, 4, 6, 12, 24, 36, 48, 60, 72, 84 (off-site phone visit) and 96 for efficacy assessment and safety monitoring, including review of adverse events and concomitant medication, vital signs, ECG, physical examination, and blood and urine specimen collections. On the day of a clinic visit at which blood samples are scheduled to be collected, approximately 10 hours (h) fasting must be confirmed prior to blood draw. On the day of the scheduled clinic visits at which there is fasting and blood is to be drawn, administration of bexagliflozin shall be withheld until after blood is drawn and taken with water at the clinic or home prior to the first meal; glimepiride shall be withheld and taken with the first meal of the day.

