5.5 Blinding

This is a double-blind, double dummy study. The sponsor, investigators, study coordinators, pharmacists, study subjects, the cardiovascular adjudication committee and the diabetic ketoacidosis committee will be blinded to the study medication.

To maintain blinding of the individual treatment assignment, the results of urinary glucose testing will not be made available to any study personnel or subjects. If knowledge of the test substance is needed to manage a subject's condition, the investigator will contact the IWRS to obtain the treatment assignment. If unblinding occurs for any reason, the time and reason for breaking the blind will be recorded on the case report form (CRF) and the sponsor must be notified within 24 h.

A designated statistician who is not involved with the study operation will hold the treatment codes. The unblinded treatment information can be provided to the DSMB to facilitate the evaluation of any clinically important increase in the rate of a serious suspected adverse reaction or to the designated safety contact when the treatment information is required to determine if an expedited safety report must be submitted to regulatory agencies.

The treatment assignment will continue to be withheld from the cardiovascular adjudication committee and diabetic ketoacidosis adjudication committee members until all global investigational studies are completed and final analyses to assess cardiovascular and ketoacidosis risks are conducted.

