5.9.2 Bexagliflozin Kit

One bexagliflozin kit contains a bottle of 90 counts of bexagliflozin tablets, 20 mg or placebo.

The label attached to each bexagliflozin kit will contain the protocol number, product identification, kit number, batch number, expiration date, subject number, investigator name, storage condition, directions for use, sponsor's name and address, and the investigational drug caution statement.

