6.13 Dispensing Investigational Product

6.13.1 Dispensing Bexagliflozin

At randomization and at every 12 weeks of treatment thereafter, each study subject will receive 1 bottle of bexagliflozin tablets, 20 mg or placebo, based on the kit number assigned to the subject by the IWRS. At visit V15, two bottles of bexagliflozin tablets will be dispensed for dosing between week 72 and week 96.

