6.13.2 Dispensing Glimepiride

Weeks 0 to 6

- Each subject will receive 1 bottle of glimepiride capsules, 2 mg or placebo, at randomization.
- During weeks 2 to 6 post-randomization, the investigator will select the glimepiride dose based on clinical assessment. The guidance for glimepiride up-titration is outlined in [Section 3.3.2.1](#). If subjects meet up-titration criteria, a bottle of glimepiride, 4 mg, 6 mg or placebo, will be dispensed. If subjects do not meet up-titration criteria, subjects will continue the glimepiride prescribed to them at the previous visit. The up-titration of glimepiride dosing can occur before the scheduled study visits in the case of persistent hyperglycemia.

Weeks 7 to 96

- From weeks 7 to 12, each subject will continue taking glimepiride prescribed to them at week 6.
- At week 12 and at every 12 weeks of treatment thereafter, each study subject will receive 1 bottle of glimepiride capsules, 2mg, 4 mg, 6 mg or placebo, based on the kit number

assigned to the subject by the IWRS. At visit V15, two bottles of glimepiride capsules will be dispensed for dosing between week 72 and week 96.

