9 PLANNED STATISTICAL METHODS

9.1 General Considerations

The following sections provide a summary of the planned analysis of the trial but a complete statistical analysis plan will be developed as a separate document and will be the final plan. All statistical analyses will be performed using SAS Version 9.2 or higher.

In general, descriptive statistics (number of subjects [N], mean, standard deviation [SD], Q1, median, Q3, minimum and maximum) will be presented for continuous variables, and frequency and percentage for categorical variables.

The primary efficacy non-inferiority test will be one-sided at 0.025 significance level. The upper bound of the 95% confidence interval (CI) on the difference of HbA1c reduction between bexagliflozin and glimepiride will be used to determine the study's conclusion. That is, if the upper bound of the CI is within 0.35%, then the primary objective of the study is met. Superiority will be declared without additional statistical testing when the upper bound of the 95% CI for the difference in change from baseline at week 60 in HbA1c comparing bexagliflozin group with glimepiride group is less than 0.

The secondary efficacy objectives will be tested at two-sided 0.05 significance level following a sequential testing procedure to control the overall type I error of 0.05. The secondary efficacy endpoints will be tested only if the primary efficacy assessment achieves significance, and following the hierarchy as below:

1. Superiority test of the change in body weight in subjects with baseline BMI ≥ 25 kg/m² in the bexagliflozin group compared with glimepiride group at week 60
2. Superiority test of the change in SBP in subjects with baseline SBP ≥ 140 mmHg in the bexagliflozin group compared with glimepiride group at week 60
3. Superiority test of the difference in proportion of subjects with ≥ 1 severe or documented symptomatic hypoglycemia events in the bexagliflozin group compared with glimepiride group over 96 weeks

The exploratory efficacy objectives and safety objectives will be analyzed descriptively.

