9.3.2 Safety Analysis Set

All subjects who are randomized and take at least one dose of double-blind study medication will be included in the Safety Analysis Set. Safety analyses will be based on the medication that was actually taken by each subject. The Safety Analysis Set is the primary analysis set for safety evaluation.

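### SAP 5.2 groups safety data by the medication taken first, protocol 9.3.2 by the medication actually taken; SAP 13 does not declare the change, and the SAP rule fails for subjects with mixed exposure

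*SAP*

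**What the plan says.** The two documents define the same safety set (randomized, at least one double-blind dose) but assign its members to treatment differently.

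- Protocol 9.3.2: "Safety analyses will be based on the medication that was actually taken by each subject".
- SAP 5.2: "Safety analyses will be based on the medication that was taken first".

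Protocol 9.1 says that "a complete statistical analysis plan will be developed as a separate document and will be the final plan", so the SAP rule is the one that would be programmed. SAP 13 lists the covariate substitutions, the retrieved-dropout primary analysis and the removal of LOCF. It is silent on this change.

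Three other features matter:

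- **Design.** Protocol 5.5: "This is a double-blind, double dummy study". Every subject takes one tablet product and one capsule product. Protocol 5.2.1 and 5.2.2 put the tablet before the first meal and the capsule with it.
- **Supply.** Kits are dispensed at up to 10 visits, V6 to V15 (Protocol 5.4, Table 2). For the tablet: "At randomization and at every 12 weeks of treatment thereafter, each study subject will receive 1 bottle of bexagliflozin tablets, 20 mg or placebo". For the capsule during titration: "If subjects meet up-titration criteria, a bottle of glimepiride, 4 mg, 6 mg or placebo, will be dispensed".
- **Counting.** SAP 9.3 counts as treatment-emergent any event that begins or worsens after the first double-blind dose. It sets no end of window and no rule for a change of treatment. SAP 6.2.6 runs patient-years from first dose to end of study by arm.

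**The concern.** An as-treated safety set exists for the few subjects whose treatment departed from their assignment. Those whose treatment changed along the way are the ones for whom these two rules can disagree. Under the SAP rule the first supply fixes a subject's column for the whole study. Since neither the event definition nor the person-time definition allows for a change of treatment, all later adverse events, laboratory values and exposure follow that first supply, even when the subject took the correct drug for most of the trial.

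At stake is the attribution of the less common events of special interest, such as ketoacidosis, where one or two subjects can alter a table. There is also a transparency problem: the analysis rule differs from the protocol with no reason given and no entry in the section meant for such changes.

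**Working it through.** **Inputs.** Treatment period: "The double-blind treatment period will start at randomization and last 96 weeks" (Protocol 3.3.2). Tablet supply: "One bexagliflozin kit contains a bottle of 90 counts of bexagliflozin tablets, 20 mg or placebo", one tablet a day (Protocol 5.9.2, 5.2.1). Planned size: 210 per arm (Protocol 9.2). Neither document gives a dispensing-error rate.

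**Step 1: reproduce the 96 weeks from the kit schedule.** Tablet bottles: 1 at V6, 5 at V10 to V14, 2 at V15, so 1 + 5 + 2 = 8. At 12 weeks each, 8 × 12 = 96 weeks, as stated. The 8 × 90 = 720 tablets cover the 96 × 7 = 672 days.

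**Step 2: when the rules differ.**

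| Exposure | Actually taken | Taken first |
|---|---|---|
| Assigned treatment throughout | assigned arm | assigned arm |
| Other treatment throughout | other arm | other arm |
| Both first kits wrong, then correct | not defined in the protocol | other arm, all weeks |
| One first kit wrong, then correct | not defined in the protocol | no arm identified |

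**Step 3: both first kits wrong.** Misreported weeks = 96 − weeks on the wrong supply, for a subject who completes treatment.

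- Error runs to the next scheduled tablet bottle at week 12: 96 − 12 = 84 weeks; 84/96 = 87.5%. The first 12 weeks are reported under what was taken.
- Error corrected after one dose: (672 − 1)/7 = 95.9 weeks, or 99.9%.

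An up-titration at week 2, 4 or 6 would replace the capsule bottle but not the tablet bottle. If that capsule bottle were correct, the subject would be in the one-kit situation of step 4 until week 12.

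**Step 4: one first kit wrong.** There are four cases:

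- Bexagliflozin subject, active capsule by mistake: both active drugs.
- Bexagliflozin subject, placebo tablet by mistake: neither.
- Glimepiride subject, active tablet by mistake: both.
- Glimepiride subject, placebo capsule by mistake: neither.

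None of these is the other study arm. Read literally, the product taken first is always the tablet, active or placebo, which names a product line and not an arm.

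**Step 5: size in a safety table.** One subject is 1/210 = 0.48 percentage points of an arm. With an assumed 0 to 3 such subjects the range is 0 to 3/210 = 1.4 points. With an assumed 10 it is 10/210 = 4.8 points.

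For person-time, assume no dropout and follow-up to week 98. An arm contributes 210 × 98 × 7/365.25 = 394 patient-years. The 84 weeks are 84 × 7/365.25 = 1.6 patient-years, or 0.41% of the arm. Ten such subjects would be 4.1%.

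**Step 6: after the fix.** If the column follows the treatment taken for most of the exposure, the step 3 subject returns to the correct arm. Misreported time falls from 84 weeks to the 12 weeks on the wrong supply (12/96 = 12.5%). Showing events by treatment at onset removes the misattribution of events in that remainder.

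**The case against.** The strongest reply is that the SAP sentence is an attempt to make the protocol workable. The protocol does not say what actually taken means for someone who took both treatments, it defers to the SAP as the final plan, and a first-dose rule is at least simple. That much stands: the protocol has a gap. But the SAP does not present its sentence as a clarification, and the rule it chose ignores everything taken after the first supply.

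A reader might infer that one wrong first bottle moves a subject's data for up to 96 weeks to the other arm, or that as little as 2% of exposure (a capsule bottle replaced after 2 of 96 weeks) decides the column. The documents do not support this. In a double-dummy trial one wrong bottle gives both active drugs or neither, so a true crossover needs both first kits wrong. If medication is read as active drug, the first active drug taken is that of the randomized arm in three of the four one-kit errors. The exception is a glimepiride subject given an active bexagliflozin tablet. The SAP does not say that this reading is meant, so the rule remains undefined there.

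It is also fair that kit numbers are assigned by the IWRS. Dosing deviations are recorded and listed (SAP 5.5, 7.2), and drug accountability and adverse events are listed by subject (SAP 19). Mixed-exposure subjects could therefore be traced. Listings limit the harm, but they do not correct the summary tables.

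**Conclusion.** The concern holds as a minor one. The two documents give different treatment-assignment rules for safety, the difference is undeclared, and the rule that would be applied misreports most of the exposure of a subject who began on both wrong kits and was then corrected. It also identifies no arm after a one-kit error.

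The 84 of 96 weeks assumes that both first kits were wrong, that the error lasted to week 12 and that the subject completed treatment. The nearly 96 weeks is the limiting case of immediate correction. The effect per subject is about 0.48 percentage points of a 210-subject arm. The number of such subjects is unknown, may be zero and is probably small.

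It would be tempting to extend the point to the hypoglycemia comparison. That does not follow: the formal test of severe or documented symptomatic hypoglycemia is a key secondary endpoint in the ITT set by randomized assignment (SAP 5.3, 8.2). Only the descriptive hypoglycemia summary in the safety set is exposed. The primary analysis and the other key secondary ITT analyses are likewise unaffected.

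**What to change.** 1. In SAP 5.2, replace the sentence with the protocol's actual-treatment rule and define it as the treatment taken for most of the double-blind exposure according to kit and accountability records. The most-of-exposure criterion is in neither document; it is proposed here to fill the protocol's gap.
2. State how one-kit errors are classified, for example kept in the randomized arm and flagged.
3. List every mixed-exposure subject, with each adverse event shown by the treatment being taken at onset.
4. Record any remaining difference from the protocol in SAP 13, before unblinding.

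The cost is a few sentences and one derivation from accountability records that Protocol 5.11 already requires. No sample size, error rate or efficacy analysis changes.
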